**Study of Adoptive Transfer of Invariant Natural Killer T Cells
Combined With TAE/TACE to Treat Unresectable Hepatocellular
Carcinoma (HCC): Phase II Clinical Trial**

NCT04011033

October 1, 2017

1. Background and Aims

Hepatocellular carcinoma (HCC) is the fifth most common cancer and a leading cause of cancer-related death among males and females of all ages ¹. It was estimated that in 2018, there were 840 thousand new liver cancer cases and 780 thousand liver cancer-related deaths in the world ¹. Of importance, unresectable HCC accounts for more than 70%~80% of the cases, limiting the possibility of achieving a cure in many patients ^{2,3}. Currently, the prognosis of HCC is poor, with a 5-year survival of about 18% even in developed countries ⁴.

Transarterial embolization (TAE) or transarterial chemoembolization (TACE) is a standard therapy for intermediate-stage HCC, which is accepted as a routine practice worldwide ^{5, 6}. Nevertheless, different clinical characteristics of HCC, such as liver function and tumor load (different size, number, and location), will lead to different responses to TA(C)E treatment and different survival times. Furthermore, repeated TACE procedures could gradually lead to TACE refractoriness, and some patients even show TACE failure ⁷. According to the Japanese Society of Hepatology (JSH) guidelines ⁸, TA(C)E failure is defined as an insufficient response after ≥ 2 consecutive TA(C)E procedures, as revealed by the response evaluation using computed tomography (CT) or magnetic resonance imaging (MRI) after 1~3 months. The median tumor doubling time after an initial response of HCC to TACE is 46 days, and $>90\%$ of the recurrent nodules have a doubling time of <3 months ⁹. The recurrence rate of intrahepatic lesions after TA(C)E is 37% and 61% at 6 and 12 months, respectively ¹⁰. Therefore, patients with HCC failed to respond to TACE,

under which circumstance is defined as TACE refractoriness, should switch to or combine with systemic therapy as soon as possible because repeated TACE is no longer beneficial for such patients ⁹.

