radiological progression. At the same time points, routine blood tests, tumor biomarkers, α -fetoprotein (AFP), and quality of life (QoL) will be measured.

After the end of treatment, the survival follow-up of the subjects will continue to be conducted every 3 months, while those who end treatment for reasons other than disease progression will undergo regular tumor imaging evaluation as much as possible after treatment, and survival follow-up must be carried out.

The details of follow-up are shown in the table below:

Project / time	Screening/ baseline period (-14d~0w)	The first cycle 3W \pm 7d	The second cycle 6w \pm 7d	Odd cycle \pm 7d	Even cycle \pm 7d	Out-of- group follow-up \pm 7d
Sign the informed consent form	×					
Medical history	×					
Inclusion / exclusion criteria	×					
Physical examination and vital signs	×	×	×	×	×	×
Blood routine	×	×	×	×	×	×
Urine routine	×	×	×	×	×	×
Biochemistry (liver and kidney function, blood glucose, blood lipid)	×	×	×	×	×	×
Myocardial enzyme	×	×	×	×	×	×
Thyroid function	×	×	×	×	×	×
Five items of hepatitis B	×					
Hepatitis C antibody	×					
HBV-DNA/HCV RNA quantification	×		×		×	×
Syphilis antibody	×					
HIV antibody	×					
Digestive tumor markers, AFP	×	×	×	×	×	×
Coagulation	×	×	×	×	×	×

Autoantibody	×					
T cell subsets	×	×	×	×	×	×
Detection of cell suspension (bacteria, fungi, endotoxin)	×	×	×	×	×	
Electrocardiogram	×		×		×	×
Colour Sonography	×					×
Liver enhanced MR or CT	×		×		×	×
Imaging data of other organs	×		×		×	×
Pathological examination of tumor	×					
Drug combination	×	×	×	×	×	×
Adverse events	×	×	×	×	×	×

The Implementation of TAE

- 1) Select catheterization of the feeding artery by using a microcatheter.
- 2) Perform abdominal and hepatic arteriography.
- 3) Embolization with Gelfoam until near stasis of the arterial flow.
- 4) Determine the dose of iodized oil by the tumor size or based on whether the portal vein had a tumor thrombosis.
- 5) Inject the emulsion of iodized oil until the accumulation of the emulsion in the tumor and the visualization of the portal vein branches near the tumor. (If there was a significant arteriportal shunt, embolization with Gelfoam was first performed to occlude the shunt, after which the iodized oil emulsion was infused, and embolization with Gelfoam was performed.)

7. Statistical Analysis

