The trial was designed to use a 2-sided 5% type I error and had 80% power to detect an improvement in PFS from 1.5 months in the TAE group to 4.5 months in the TAE-iNKT group, corresponding to a hazard ratio (HR) of 0.33 in terms of median PFS. In consideration of these assumptions, the trial design was powered for 60 patients to be randomly assigned in each group as the intention-to-treat population (allocation ratio of 1:1, n=30 patients in each group), and allowing for a drop-out rate of 20%. Sample size estimation was performed using PASS 11.

Continuous variables will be expressed as the median and IQR, and will be compared using t tests or Mann-Whitney tests. Categorical variables will be presented as the frequency and percentage, and will be compared using Fisher's exact tests. Survival and time to QoL deterioration will be estimated using the Kaplan-Meier method, and their 95% CIs will be calculated using the Brookmeyer and Crowley method. Survival differences will be compared using log-rank tests. Peripheral blood cells will be analyzed using Sidak's multiple comparison test. The overall two-sided significance level of $P < .05$ will be split into a two-sided significance level of $P < .01$ for tests of PFS, OS, ORR, DCR, and QoL according to the Bonferroni method (dividing the available total α (typically 0.05) equally among the chosen endpoints). If the PFS and/or all secondary endpoints are statistically significant at a two-sided significance level of 0.01, the curative effect of TAE-iNKT will be deemed better than that of TAE alone. All statistical analyses will be conducted using SAS software version 9.4 (SAS Institute).

8. Data Management.

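### No hazard ratio is planned for PFS, and its only between-group test ignores baseline factors that the plan itself says affect outcome

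*Combined protocol and SAP*

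**What the plan says.** Section 7 (Statistical Analysis) plans Kaplan-Meier estimates with 95% Brookmeyer-Crowley intervals, and for the comparison of arms: "Survival differences will be compared using log-rank tests". No Cox or other model, stratified test, covariate or estimated HR appears anywhere.

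The sample size rests on a target effect given as "improvement in PFS from 1.5 months in the TAE group to 4.5 months in the TAE-iNKT group". In relative terms, the plan describes this target as "corresponding to a hazard ratio (HR) of 0.33 in terms of median PFS". The design statement reads "The trial was designed to use a 2-sided 5% type I error and had 80% power", but under the Bonferroni split the efficacy claim needs a result "statistically significant at a two-sided significance level of 0.01".

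Section 1 (Background and Aims) says that characteristics of the disease, "such as liver function and tumor load (different size, number, and location), will lead to different responses". The same sentence names survival as a second outcome that varies with them. These factors are known before treatment:

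- Child-Pugh A or B is an entry criterion in Section 3.
- Section 6 has all target and non-target lesions imaged at baseline.
- The follow-up table in Section 6 has liver biochemistry and "Digestive tumor markers, AFP" at screening.

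Section 6 randomises 1:1 from a random number table and states no stratification.

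**The concern.** Two separate things are missing.

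The first is the effect estimate. The trial is built around an HR, but the planned output for PFS is a p-value and two curves with their medians. Readers could not compare the result with the design HR of 0.33 or see how precise it is.

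The second is efficiency. The plan says that liver function and tumour load matter, yet neither the randomisation nor the analysis uses them. When strong prognostic factors are left out of a time-to-event comparison, the unadjusted treatment contrast shrinks towards no effect and power falls. With 30 patients per arm, chance imbalance also makes a single result harder to interpret. If 30% are assumed to be Child-Pugh B, the arms differ by 15 percentage points or more in about 20% of trials.

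**Working it through.** **Inputs from the documents.** Median PFS 1.5 and 4.5 months; two-sided alpha 0.05 for sizing and 0.01 for testing; power 80%; "allocation ratio of 1:1, n=30 patients in each group), and allowing for a drop-out rate of 20" percent. Section 7 mentions both 60 and 30 per group; I read 60 in total.

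**Step 1: the plan's own figures.** The HR is 1.5/4.5 = 0.333, as stated. For the sample size:

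- Schoenfeld: events = 4(z_a + z_b)²/(ln HR)². At 0.05 this is 4(1.960 + 0.842)²/1.207 = 26.0, so 27 events, and 27/0.8 gives 34 patients.
- Freedman: events = (z_a + z_b)²[(1 + HR)/(1 - HR)]². At 0.05 this is 7.85 × 4 = 31.4, so 32 events and 40 patients.
- Freedman at 0.01: 11.68 × 4 = 46.7, so 47 events and 59 patients.

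The stated alpha of 0.05 does not give 60 by these formulas. Freedman at 0.01 comes close, as does Freedman at 0.05 with an assumed fixed follow-up of about 4 months (60 to 63). This mismatch is a separate issue, but it is why power is shown at both levels below.

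**Step 2: log-rank against adjusted Cox.** The documents give no covariate effects, so these are assumed. Settings: 60 patients; exponential PFS with arm medians held at 1.5 and 4.5 months; 24-month cut-off; 20% of patients given an early censoring time, uniform over 0 to 6 months; Child-Pugh B in 30%; a continuous tumour-load score; 3,000 runs per row; about 51 to 53 events. Simulation error is at most √(0.25/3000) = 0.9 points per power figure.

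| Assumed strength (HR for Child-Pugh B; HR for load per SD) | Log-rank, 0.01 | Cox, 0.01 | Change | Log-rank, 0.05 | Cox, 0.05 | Median HR, unadjusted |
|---|---|---|---|---|---|---|
| None (1; 1) | 90.6% | 88.1% | -2.5 | 97.5% | 96.6% | 0.33 |
| Weak (1.5; 1.3) | 84.6% | 86.7% | +2.1 | 94.8% | 96.4% | 0.35 |
| Moderate (2.0; 1.5) | 77.2% | 86.6% | +9.4 | 90.9% | 95.8% | 0.38 |
| Strong (3.0; 2.0) | 60.3% | 86.0% | +25.7 | 80.5% | 95.8% | 0.44 |

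The adjusted HR has a median of about 0.32 in every row (true conditional value 0.333).

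**Step 3: other settings, at 0.01.**

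- Three covariates, scans on the Section 6 text schedule, Efron ties: 70% to 81% (Child-Pugh B 2.0, the other two 1.4 per SD); 84% to 85% (1.5, 1.2, 1.2).
- Three covariates in another set of runs: 89.0% to 86.9% with no effect; 87.4% to 88.0% when weak (Child-Pugh B 1.3, AFP 1.2 per SD); about 80% to 87-88% when moderate, or 77% to 84% with scheduled scans.
- Child-Pugh (B in 35%) and AFP only: 76% to 84% (2.0, 1.4 per SD); 67% to 83% (2.5, 1.6). At a true treatment HR of 0.45: 43% to 52%.

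The largest loss with non-prognostic factors was about 3.5 points.

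**Step 4: type I error.** With three covariates, scheduled scans and 5,000 null runs, it was 1.1% for both tests at 0.01, and 5.2% (log-rank) and 5.1% (Cox) at 0.05. With two covariates and 3,000 runs it was 6.0% and 5.9% at 0.05, with a simulation error of about 0.4 points. Adjustment did not raise it.

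**Step 5: ties.** Progression is dated only at scans. A control median of 1.5 months is about 6.5 weeks. Under an exponential curve, 1 - 0.5^(4/6.5) = 35% of controls would have progressed by a week-4 scan, about 10 of 30 sharing one date. With the Breslow approximation, adjusted power in the 70%-to-81% setting fell to 68% and the HR shrank to 0.39; with Efron the HR was 0.33. The Section 6 text (every 4 weeks at first) and its follow-up table (even cycles, the second at week 6) give different scan times, but ties arise under either.

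**Step 6: what an interval would show.** With 60 × 0.8 = 48 events, the SE of log HR is about 2/√48 = 0.289. Around 0.333, the 99% interval is 0.333 × exp(±2.576 × 0.289), or 0.16 to 0.70. The 95% interval is 0.19 to 0.59.

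**The case against.** The strongest reply is that the planned test is sound. Under 1:1 randomisation the unadjusted log-rank test controls type I error, and chance imbalance is already allowed for in it. It also matches the usual sizing method for a PFS comparison. That stands. A reader might infer that the PFS test is biased or invalid, and nothing in the documents supports that.

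Second, the gain in power is assumed. Section 1 gives no effect sizes, and the entry limits (BCLC B, Child-Pugh A or B) may narrow the spread of risk. This also stands: a flat statement that adjustment will raise power goes too far. With weak factors the gain is negligible, and with none there is a small loss. At 0.05, power stays at or above the planned 80% in every row of the table. The lower figures at 0.01 partly reflect sizing at one alpha and testing at another, and that part should not be blamed on the missing covariates.

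Third, any Cox model, even without covariates, would supply an HR, and an adjusted HR is not the design quantity. The design HR is a ratio of arm medians, whereas an adjusted HR is conditional on the covariates. The two agree in the exponential simulation but need not in general. So it would be wrong to say that adjustment is needed to obtain an HR, or that it recovers the design HR by definition.

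Fourth, Kaplan-Meier estimates are also planned, so the log-rank test is the only between-group comparison of PFS, not the only PFS analysis. The 95% intervals on single-arm medians are descriptive and do not conflict with a test at 0.01.

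What remains is that no effect estimate is planned, and that baseline information the plan itself calls relevant goes unused.

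**Conclusion.** The concern holds as a gap in estimation and a probable loss of efficiency. It does not show a failure of error control. The missing HR and interval follow directly from Section 7 and need no assumption.

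The case for adjustment depends on Section 1 being right about liver function and tumour load. At two-sided 0.01 the change in power is about -2 to -3.5 points if they are not prognostic, +1 to +2 if weak, +7 to +11 if moderate and about +26 if strong. These ranges assume 30 patients per arm, a true HR of one third, exponential PFS, 20% early drop-out and the covariate effects listed above. The exposure is lopsided in favour of adjusting: a small loss if Section 1 is wrong, against a moderate to large gain if the factors are at least moderately prognostic. The change is advisable, but the trial is interpretable without it.

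**What to change.** Before any outcome is compared by arm, and at the latest before database lock, add to Section 7:

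- A Cox model as the primary PFS analysis, with treatment, Child-Pugh class and baseline sum of viable target-lesion diameters. Log AFP may be a third covariate; it is optional because Section 1 does not name it. Use the same model for OS.
- Efron or exact handling of ties, named in the text and not left to a software default.
- The HR with an interval at the level of the test: 99% if PFS is tested at 0.01.
- A sentence saying that the adjusted HR is conditional, whereas the design HR is a ratio of medians.
- The unadjusted log-rank test as a sensitivity analysis.

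If the sponsor prefers to keep the log-rank test as primary, the HR and its interval should still be reported.

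The cost is a paragraph of SAP text and a few lines of SAS. No new measurement is needed, but Child-Pugh class has no row in the follow-up table, so the case report form should be checked to confirm that it is recorded. With about 50 events the model should hold no more than two or three covariates. The price is the small loss of power if they turn out not to be prognostic.

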1) the use of research drugs is not consistent with the clinical regimen, and has a significant impact on the evaluation of efficacy and safety, 2) those without any record, 3) those who did not take research drugs.

TACE Failure Criteria:

1) Intrahepatic lesion [i, two or more consecutive ineffective responses seen within the treated tumors (viable lesion >50%), even after changing the chemotherapeutic agents and/or reanalysis of the feeding artery, on response evaluation CT/MRI after 1–3 months following adequately performed selective TACE. ii, two or more consecutive progressions in the liver (including an increase in the number of tumors compared to that before the previous TACE procedure), even after changing the chemotherapeutic agents and/or reanalysis of the feeding artery, on response evaluation CT/MRI after 1–3 months following adequately performed selective TACE]. 2) Continuous elevation of tumor markers right after TACE, even though transient minor reduction is observed. 3) Appearance of vascular invasion. 4) Appearance of extrahepatic spread.

4. Endpoints and Definitions

The primary endpoint is the PFS, i.e., the time from enrollment to disease progression according to the modified RECIST (mRECIST) guideline in trial immunotherapeutics, or death from any cause, whichever occurred first. Secondary endpoints include overall survival (OS), objective response rate (ORR), disease control rate (DCR), quality of life (QoL), and safety. Patients without any post-baseline tumor assessment are considered non-responders. Objective responses

will be confirmed at least 28 days after the initial documentation of the response.

Progression-Free Survival: Time from the date of enrollment to the date of first documentation of tumor progression.

Progression was defined using Modified RECIST (mRECIST): an increase of at least 20% in the sum of the diameters of viable (enhancing) target lesions, taking as reference the smallest sum of the diameters of viable (enhancing) target lesions recorded since treatment started.

Overall survival: time from the date of enrollment to the date of death from any cause.

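### Testing five endpoints at a fixed 0.01 each is valid but avoidably inefficient: Holm's step-down procedure keeps the same 5% familywise error and never rejects fewer

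*Combined protocol and SAP*

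**What the plan says.** Section 7 (Statistical Analysis) fixes the multiplicity rule in two steps. First, the overall two-sided 5% is shared out, at 0.01 apiece, "for tests of PFS, OS, ORR, DCR, and QoL according to the Bonferroni method". The shares are the same for all five, because the total is spread "equally among the chosen endpoints". Second, the decision sentence repeats the fixed level: "If the PFS and/or all secondary endpoints are statistically significant at a two-sided significance level of 0.01", TAE-iNKT is to be declared better than TAE alone.

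Section 4 gives the endpoints their rank: "The primary endpoint is the PFS", and "Secondary endpoints include overall survival (OS), objective response rate (ORR), disease control rate (DCR), quality of life (QoL), and safety". Safety is therefore a secondary endpoint outside the five-test family. No step-down, hierarchy, gatekeeping or reuse of alpha appears anywhere.

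Section 7 also names Fisher's exact test for categorical variables, which covers ORR and DCR, and the log-rank test for survival differences. It gives 30 patients per group and a 20% drop-out allowance. It states no effect size for OS, ORR, DCR or QoL.

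**The concern.** Under the single-step rule each endpoint must reach 0.01 whatever the others show. If PFS succeeds, its 0.01 share of the 5% is not passed on. With 30 per group the other four comparisons are likely to be short of power, and they are the ones that could use it. A rule that never rejects fewer hypotheses at the same familywise error is available and needs no further assumption about how the endpoints are correlated. That matters here because PFS, ORR and DCR all rest on the same mRECIST measurements. At stake are the individual claims on OS, ORR, DCR and QoL, not the validity of the trial.

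**Working it through.** **1. The plan's own figure.** 0.05/5 = 0.01, which reproduces exactly. The sample size also fits this level. Freedman's formula at HR 0.33, two-sided 0.01 and 80% power gives (2.576 + 0.842)² × (1.33/0.67)² = 11.68 × 3.94 = 46.0, which the calculation takes up to 47 events, or 24 per arm. Then 24/(1 − 0.20) = 30 per arm. Section 7 does not name the formula used, and it attributes the size to a 5% type I error ("The trial was designed to use a 2-sided 5% type I error and had 80% power"). Freedman at 5% gives only 31 to 32 events and a total of 39 to 40. So 60 patients is consistent with PFS at 0.01, which is also Holm's first threshold, and the change needs no extra patients.

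**2. Dominance, with no assumptions.** Holm compares the j-th smallest of five p-values with 0.05/(6 − j): 0.0100, 0.0125, 0.0167, 0.0250, 0.0500, stopping at the first failure. Every threshold is at least 0.01, so any p-value at or below 0.01 is rejected under both rules. Holm controls familywise error at 5% under any dependence.

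**3. Check by simulation.** 400,000 equicorrelated normal draws per setting, correlation 0, 0.3 and 0.6. No Bonferroni rejection was ever lost.

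| Familywise error | Bonferroni | Holm |
|---|---|---|
| All five null | 4.9 / 4.7 / 3.9% | 4.9 / 4.7 / 3.9% |
| PFS effective, four null | 4.0 / 3.8 / 3.3% | 4.9 / 4.7 / 4.0% |

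**4. Size of the gain, under assumed effects.** The effects and event counts for the secondaries are assumptions. Mean of a log-rank statistic: |ln HR| × √events / 2. PFS: HR 1/3 with 48 events (60 × 0.80) gives 1.099 × √48/2 = 3.81.

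- *Large effects.* OS HR 0.5, 35 deaths: 2.05. QoL deterioration HR 0.45, 30 events: 2.19. ORR 20% vs 50% and DCR 50% vs 80%: exact Fisher power with 30 per arm is 35% at 0.01 and 60% at 0.05, so the mean is set to 2.576 − 0.385 = 2.19 to match the 35%.
- *Modest effects.* OS HR 0.7: 1.06. QoL HR 0.65: 1.18. ORR 20% vs 40%: 0.20/√((0.16 + 0.24)/30) = 1.73. DCR 50% vs 70%: 0.20/√((0.25 + 0.21)/30) = 1.62.

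| Correlation 0.3 | Bonferroni | Holm |
|---|---|---|
| Large: OS/ORR/DCR/QoL power | 30/35/35/35% | 40/44/44/44% |
| Large: all four secondaries | 5% | 18% |
| Large: PFS or all secondaries | 89.2% | 90.5% |
| Modest: OS/ORR/DCR/QoL power | 6/20/17/8% | 9/24/21/11% |
| Modest: all four secondaries | 0.4% | 2.4% |
| Modest: PFS or all secondaries | 89.0% | 89.4% |

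Across the three correlations the gain per secondary endpoint is about 9 to 11 points (large) and 2 to 5 points (modest). The modest ORR and DCR figures use a normal approximation. Set to their Fisher power of 11% at 0.01, the gains are 2 to 4 points. The chance of meeting the success rule rises by 0 to 2.4 points.

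**5. Sensitivity.** With PFS power at 80% instead of 89%, the large-effect gain in the success rule reaches 3.8 points (80.2% to 84.0%, correlation 0). If, in addition, every secondary had 80% power at 0.05, it reaches 6.7 points (82.4% to 89.1%, correlation 0). The chance of at least one rejection is the same for both rules in every setting, because both start at 0.01.

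**The case against.** The strongest reply is that nothing here is wrong. The equal split is prespecified, simple and controls familywise error. Holm is only one alternative, and it treats the five endpoints as exchangeable although PFS is primary; a fixed sequence or gatekeeping scheme would respect the ranking. This stands in part: the choice among valid procedures is a judgement. But a fixed sequence can lose rejections that the present plan would make, and Holm cannot.

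A reader might infer that the secondary endpoints lose power for nothing. The documents do not support that. Section 6 continues survival follow-up every 3 months after treatment, and no common analysis date is stated. Under the present rule each endpoint can be tested at 0.01 when its data mature. Under Holm, a p-value above 0.01 stays unresolved until enough of the others are known. That is a real cost, as are less simple simultaneous intervals, though Section 7 plans only 95% intervals and so makes no use of Bonferroni's 99% ones.

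A reader might also infer a large gain. With a normal approximation for ORR 20% vs 50%, power appears to go from 50% to 59%, and the chance that all five endpoints are significant from 8% to 24% (correlation 0.3). These figures do not fit the plan: it names Fisher's exact test, for which power at 0.01 is 35%, and 60% is reached only at the full 0.05. They also rest on effects that the documents nowhere state.

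**Conclusion.** The point holds as an inexpensive improvement to a valid plan. The dominance of Holm over single-step Bonferroni needs no assumption. Its size does: about 2 to 5 points of power per secondary endpoint with modest effects and 9 to 11 with large ones, conditional on the effect sizes, event counts and correlations assumed above.

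It would be wrong to conclude that the plan inflates type I error or that the trial's main conclusion is likely to change. If the decision sentence is read as PFS or all secondaries, the success probability moves by about 0 to 3 points in the two scenarios with PFS power near 89%. It moves by more only under the less favourable PFS power and stronger secondaries shown in the sensitivity check. The benefit lies in the separate claims on OS, ORR, DCR and QoL.

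**What to change.** Before outcome data are seen, amend Section 7 in three places.

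- Replace the Bonferroni sentence with: *PFS, OS, ORR, DCR and QoL are tested with Holm's step-down procedure at an overall two-sided 5%.*
- In the decision sentence, replace the fixed 0.01 level with *by the Holm procedure*. Otherwise naming Holm changes nothing.
- State that Holm-adjusted p-values will be reported.

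Two further items must be settled for this to run. Name one prespecified analysis time from which all five p-values are taken. Name the single QoL test that enters the family, since Section 4 gives both a QLQ-C30 group comparison and time to deterioration; Bonferroni needs this as well.

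The cost is a short amendment, with no extra patients, data or software. In exchange the sponsor gives up testing each endpoint independently as it matures and accepts less simple simultaneous intervals. If early separate testing of PFS or response matters more than secondary power, keeping Bonferroni is defensible, and the plan should say so.
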